5.5 Missing Data

In general, missing values will be treated as such, no imputation will be performed. The number of missing values will be reported.

Missing information about tumour response at EOS will be censored on the day of the last available adequate assessment or at randomisation (See Section 3.4.1 for full censoring rule details).

Missing HRQL data will be handled according to the QoL questionnaire manuals.

Regarding partial dates, imputation was done as follows by the data management team directly in the clinical database according to the data management plan (version 2.0):

Partial dates were only imputed in the clinical database for the following dates where at least the year was provided:

- Medical history (MH) and Surgical history (SH) start and stop dates
- Previous Therapy/Post study Follow up treatment
- Tumour Histology
- AE start and resolution dates
- Concomitant Medication
- Somatostatin analogues medication

Incomplete dates in other fields resulted in a query being raised. The imputations derived for the above-mentioned dates were conducted as follows:

- Missing days defaulted to the first of the month for start dates and the last day of the month for stop dates.

ITM-LET-01	Statistical Analysis Plan
-------------------	----------------------------------

- Missing months defaulted to the first month (January) for start dates and to the last month (December) for stop dates.
- There was no default for a missing year field.

Incomplete or incorrect times resulted in a query being raised. The imputations derived for confirmed unknown times were as follows: Unknown times defaulted to 00:00.

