3.4 Study Variables

3.4.1 Primary Variable

Progression-free survival

Progression-free survival will be determined starting from randomisation until the date of an event (PD or death). For the primary analysis, any withdrawal (or drop-out) before EOS visit at month 30 will be censored. Patients who have not shown progression at the end of the study (30 months) will also be censored.

In more details, the following rules will be applied for the main PFS analysis:

ITM-LET-01	Statistical Analysis Plan
------------	---------------------------

Table 1: PFS analysis rules

Situation	Date of Progression or Censoring	Outcome
Tumour progression or death	Earliest date of PD or death	Event (PD or Death)
No tumour progression and not death	Date of last adequate* radiological assessment	Censored
Unless:		
No baseline radiological tumour assessment	Date of randomisation	Censored
No adequate post-baseline radiological assessment and date of death, if any, is after 2 or more scan intervals following randomization**	Date of randomisation	Censored
New anticancer treatment started prior to tumour progression or death (whichever is earlier)	Date of the last adequate radiological assessment prior to start of new anticancer treatment or date of randomization (whichever is later)	Censored
Tumour progression or death documented immediately after 2 or more consecutive missing scan** following last adequate radiological tumour assessment or randomization (whichever is later).	Date of last adequate radiological tumour assessment or date of randomisation (whichever is later).	Censored

Table footnotes:

**Adequate radiological tumour assessment refers to an assessment with one of the following responses: CR, PR, SD, or PD.*

***The interval is higher than 2 times the maximal protocol scheduled RECIST 1.1 assessment interval (i.e. >222 days = 2*(90+21))*

For primary endpoint (PFS) main analysis, post-randomisation tumour assessment based on blinded central review compare to baseline will be used.

Where appropriate, sensitivity analyses will explore the impact of the chosen approaches and data issues observed during the blind review on the study results. These could include but not limit to:

- Blinded central RECIST 1.1 evaluation (main analysis) vs. Local RECIST assessments
- Applied main PFS censoring rules (main analysis, see Table above) vs. different approaches (e.g. next scheduled assessment date instead of date of radiological

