17.7.3.1 Adverse Events

Adverse event (AE): Any untoward medical occurrence in a patient or clinical investigation subject administered a pharmaceutical product and which does not necessarily have a causal relationship with this treatment. By definition, all AEs in the rollover period are regarded as 'treatment emergent', i.e., not seen before the first administration of ¹⁷⁷Lu-edotreotide PRRT or, if already present before treatment, worsened after start of treatment.

Events/Conditions prior to the first dosing administration of ¹⁷⁷Lu-edotreotide PRRT will be captured for all rollover patients and reported separately from treatment emergent AEs (TEAEs), as rollover baseline findings.

If the rollover baseline finding is "continuing" into the rollover period, no AE is to be recorded if, after start of dosing administration of ¹⁷⁷Lu-edotreotide PRRT, the event has the same or

milder pattern and intensity/severity. If the finding worsens in terms of either the pattern or intensity/severity after study drug administration, the event must be documented as an AE.

If the onset date of an AE is not recorded and if the onset date of an AE occurring after the first drug administration cannot be excluded, then, the AE is considered as TEAE. An AE, having been absent pretreatment, or worsens relative to the pretreatment state is also considered as TEAE.

Refer to Section 8.3.2 of the protocol for details on assessing and reporting AEs, as applicable to treatment with ¹⁷⁷Lu-edotreotide PRRT during the rollover extension.

All deaths, AEs and other significant AEs will be listed.

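### Partial start dates of next therapy are imputed to the earliest possible date with no floor at progression, so a documented PFS event can become a censored case

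*SAP*

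**What the plan says.** SAP 5.5 (Missing Data) says that partial dates with at least a year were imputed by data management in the clinical database itself. For days: "Missing days defaulted to the first of the month for start dates and the last day of the month for stop dates". For months: "Missing months defaulted to the first month (January) for start dates and to the last month (December) for stop dates". The fields covered include "Previous Therapy/Post study Follow up treatment", concomitant medication and "AE start and resolution dates". Incomplete dates in fields not on the list are queried instead. For clock times confirmed as unknown: "Unknown times defaulted to 00:00".

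SAP 3.4.1, Table 1, has a row for "New anticancer treatment started prior to tumour progression or death (whichever is earlier"). Such a patient is censored at the last adequate scan before the new treatment started, or at randomisation if that is later.

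No text in either section says that an imputed treatment start may not precede a documented progression (PD). The PFS sensitivity analyses named after Table 1 do not mention imputed dates.

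**The concern.** Each rule is ordinary by itself. Together they let an administrative default decide whether a progression counts. Patients leave the study at progression (Protocol 4.7) and may start a next therapy soon afterwards. Further treatments are then collected by site contact about every six months (Protocol 7.4.1), a setting in which incomplete start dates are plausible. Moving a start date to the earliest compatible day can place it before the progression that led to it.

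The error runs one way: an earlier treatment start can delete a PFS event but never create one. It also acts at the moment of progression, so the resulting censoring is informative. Options after progression differ by arm, since patients progressing on everolimus may be offered 177Lu-edotreotide (Protocol 7.4.2), so an unequal loss of events cannot be ruled out. The primary confirmatory endpoint is the one affected.

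**Working it through.** **Inputs.** Imputation rule: SAP 5.5. Censoring rule: SAP Table 1. Design: 180 events, HR 0.6471 (medians 11 and 17 months), 2:1 allocation, two-sided 5%, 80% power (SAP 4). Final critical value 2.014 (SAP Table 3). The SAP does not name the field that feeds the new-treatment row; I take it to be post-study follow-up treatment. The share of partial dates and the lag from PD to next therapy are not given and are assumed throughout.

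**1. The plan's own figure.** Schoenfeld power at 180 events, with allocation factor (1/3)(2/3) = 2/9:
√(180 × 2/9) × |ln 0.6471| − 1.960 = 6.325 × 0.4353 − 1.960 = 0.793, and Φ(0.793) = 78.6%. This is within two points of the stated 80%.

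**2. One case.** PD is on 10 March. Next therapy starts on 25 March, but only the month is recorded. The start becomes 1 March, which precedes PD, so the patient is censored at the last adequate scan before 1 March. If only the year is known, the start becomes 1 January and censoring moves to a scan before that date.

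**3. Chance that a partial date flips an event.** Take PD on day d of a month of M days and therapy L days later. With the day missing, the event flips if therapy falls in the same month (d + L ≤ M) and PD was not on the 1st (d ≥ 2). That gives M − L − 1 of M days. With mean M = 365.25/12 = 30.44:
- L = 7: 22.44/30.44 = 74%
- L = 14: 15.44/30.44 = 51%
- L = 21: 8.44/30.44 = 28%
- L = 28: 1.44/30.44, about 5%
- L = 42 or more: 0%

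With the month missing (start set to 1 January), the chance is (365.25 − L − 1)/365.25:
- L = 14: 96%
- L = 60: 83%
- L = 180: 50%

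Enumerating every PD date from 2018 to 2021 gives the same percentages.

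**4. Effect of losing events.** Schoenfeld power at HR 0.6471 is 78.6% with 180 events, 76.5% with 171 (5% lost) and 74.3% with 162 (10% lost).

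A simulation used 3,000 trials, 100 vs 200 patients, exponential medians of 11 and 17 months, 3-monthly scans, 30 months of follow-up and 15% dropout. A flipped event was censored one scan earlier, and power was counted at the 2.014 boundary.

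| Events flipped, everolimus / PRRT | Mean HR | Power | Events |
|---|---|---|---|
| 0% / 0% | 0.648 | 0.837 | 211 |
| 5% / 5% | 0.645 | 0.834 | 200 |
| 10% / 10% | 0.644 | 0.808 | 190 |
| 10% / 5% | 0.677 | 0.734 | 196 |
| 5% / 10% | 0.615 | 0.892 | 194 |

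Equal flipping mainly costs events. Unequal flipping moves the HR in favour of the arm that loses more of them.

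**The case against.** **Size.** A reader might infer a definite number of lost events. Suppose 80% of progressors start a new therapy, 10% of start days are missing, and lags are exponential with mean 30 or 60 days. About 36% or 21% of day-missing starts then flip, giving 0.36 × 0.80 × 0.10 × 180 = 5.2 or 0.21 × 0.80 × 0.10 × 180 = 3.0 events. The documents support none of these inputs, and the exponential shape puts most weight on the shortest lags. With the same means but a 14-day minimum lag, the shares fall to about 19% and 8%, or 2.7 and 1.2 events. Very short lags are also unlikely for everolimus patients moving to PRRT, who need an end-of-study visit, consent and a named-patient request (Protocol 7.4.2) for a product made to individual order (Protocol 5.1.3). The 180 events include deaths, which a later therapy cannot flip. This objection stands: no count can be claimed.

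**Other mitigation.** PFS uses the central read, while patients leave on local PD. If therapy truly starts before central PD, Table 1 censors the case whatever the imputation. The final analysis is triggered by 180 events or by all patients reaching end of study (SAP Table 3), so the first effect of lost events may be a later cut. The list of sensitivity analyses is open-ended. All of this is fair, but none of it supplies the missing floor.

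**Adverse events.** A reader might also infer that the same rule, with the midnight default, moves on-treatment events to baseline, so that treatment-emergent events are under-counted, and that the rollover section applies the opposite rule. The documents do not show this. Events are recorded as baseline findings or AEs according to whether they began or worsened before or after first dose (Protocol 8.3.1.1 and 8.3.1.2), and Protocol 8.3.2.1 treats all AEs as treatment emergent by definition. SAP 8.1 reports pre-treatment events separately, but nothing reclassifies a recorded AE by an imputed date or a default time. The rollover text (SAP 17.7.3.1) concerns onsets that were not recorded: "if the onset date of an AE occurring after the first drug administration cannot be excluded, then, the AE is considered as TEAE". That is a classification rule, and it can coexist with the imputation rule.

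**Conclusion.** The PFS point holds as a gap in the rules. Followed as written, SAP 5.5 and Table 1 can convert a documented progression into a case censored at an earlier scan. It applies only to partial start dates where therapy began after PD in the same calendar month (day missing) or calendar year (month missing). It can only remove PD events.

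The frequency and any imbalance between arms are unknown, so the figures above are illustrative. Under equal flipping of up to 10%, the HR stays at 0.644 to 0.648. The larger shifts, to 0.677 or 0.615, need an imbalance that no document establishes, and the direction is not fixed. For adverse events only a clarification is warranted. Should be fixed, with moderate confidence.

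**What to change.** Before results are seen, change the PFS derivation in the SAP:

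- Keep the raw partial start date of new anticancer therapy, or recover it, with an imputation flag in the analysis dataset.
- Do not let an imputed start precede a documented PD unless the known date parts force it. If the recorded month or year is compatible with a start on or after PD, the PD stands as an event. The step 2 case then remains an event.
- Add a sensitivity analysis of PFS using the earliest and the latest possible start dates, and report by arm how many outcomes change.

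For adverse events, add one clarifying sentence to SAP 8.1: an imputed date or a default time does not move a recorded AE to baseline when onset on or after first dose cannot be excluded.

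The cost is SAP wording and a derivation change. Because imputation was done in the database, raw dates may have to be recovered from the audit trail described in Protocol 10.3; the documents do not say whether they remain in the exported data.

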5.6 Baseline Definition

Unless stated otherwise:

- for demographic parameters, tumour assessment, QoL, biomarkers and in general all efficacy related variables, baseline is defined as the last non-missing measurement on or prior to randomisation date.
- for lab, vital signs and in general all safety related variables, baseline is defined as the last non-missing measurement prior to first dosing of study treatment.

5.7 Interim Analyses and Multiple Testing

Per the Protocol, a three-stage group sequential design, including two interim analyses to assess the primary efficacy endpoint (Progression Free Survival: PFS) after 90 and 135 PFS events have occurred will be performed, using an O'Brien Fleming alpha spending approach.

To take multiple testing into account, i.e. to keep the overall alpha level of 5%, the primary and key secondary endpoints will be tested in a strictly hierarchical procedure:

The primary endpoint (PFS) will be tested using O'Brien-Fleming type boundaries applied on the information time point as presented in the table below first.

Table 3: PFS interim analysis information time points and significant thresholds

	First PFS Interim Analysis	Second PFS Interim Analysis	Final PFS Analysis
Conducted after	90 PFS events occurred	135 PFS events occurred	180 PFS events occurred*
Two-sided Local Significance Level according to O'Brien Fleming alpha spending	0.0031	0.0183	0.044
Upper critical boundary according to O'Brien Fleming alpha spending	2.963	2.359	2.014

* Or all randomized patients reach EOS

Note: Calculations were made using the "rpact" R package developed according to the methods described in the monograph by Wassmer and Brannath (2016).

If the PFS test results in a significant p-value (i.e. $p < x.xxx$, see the table above for significance levels at each interim analyses), a confirmatory test for the ORR will be performed with a similar approach using O'Brien-Fleming type boundaries calculated extemporaneously based on the number of evaluable patients at the time of the interim analysis compared to the 300 patients to be randomised (see examples of different possible scenarios at the first PFS interim analysis in Table 4 below). Otherwise the test for ORR is considered exploratory.

Table 4: Examples of O'Brien-Fleming type boundaries calculated for the first interim analysis time point of the ORR

Number of Randomised patients evaluable in the ORR analysis at the first significant PFS interim analysis	100	150	180	200	220	230	240	250	280	300
Information time point (basis: 300 randomised patients)	33.3%	50.0%	60.0%	66.7%	73.3%	76.7%	80.0%	83.3%	93.3%	100.0%
Two-sided Local Significance Level according to O'Brien Fleming alpha spending	0.0002	0.0031	0.0076	0.0121	0.0177	0.0209	0.0244	0.0282	0.0407	0.05
Upper critical boundary according to O'Brien Fleming alpha spending	3.711	2.963	2.669	2.509	2.371	2.309	2.250	2.195	2.047	1.96

Note: The actual critical boundaries for ORR will be calculated at the time of the interim analysis according to the number of randomised patients evaluable for ORR over an estimated total 300 patients to be randomised. Calculations were made using the "rpact" R package developed according to the methods described in the monograph by Wassmer and Brannath (2016).

A confirmatory test for OS will only be performed if both previous tests (i.e. PFS and ORR) resulted in significant p-values. The actual O'Brien-Fleming type critical boundaries for OS will be calculated at the time of interim according to the number of OS events actually observed over an estimated total of 198 death events (See examples of different scenarios in the table below). Otherwise, the test for OS is considered exploratory.

Table 5: Examples of O'Brien-Fleming type boundaries calculated for the first interim analysis time point of OS

Number of OS events observed at the first significant PFS and ORR interim analysis	20	30	35	40	45	50	60	70	80	90
Information time point (Basis: 198 OS events)	10.1%	15.2%	17.7%	20.2%	22.7%	25.3%	30.3%	35.4%	40.4%	45.5%
Two-sided Local Significance Level according to O'Brien Fleming alpha spending	<1E-07	<1E-07	1.96E-07	1.23E-06	5.16E-06	1.64E-05	9.33E-05	0.0003	0.0008	0.0018
Upper critical boundary according to O'Brien Fleming alpha spending	6.956	5.640	5.203	4.851	4.558	4.310	3.907	3.593	3.338	3.126

Note: The actual critical boundaries for OS will be calculated at the time of the interim analysis according to the number of OS events observed over an estimated total 198 deaths. Calculations were made using the "rpact" R package developed according to the methods described in the monograph by Wassmer and Brannath (2016).

The tests on variables other than PFS, ORR, and OS will only be considered exploratory and performed on 5% significance levels.

The interim results sharing policy and procedure is described in the Interim Analysis Result Sharing Plan attached to this SAP.

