3.1 General Study Design and Plan

Phase: III, multi-centre

Study configuration and experimental design: confirmatory, prospective, parallel group

Type of control: active drug

Blinding: open-label

Treatment assignment: 300 GEP-NET patients randomised in a 2 : 1 fashion to receive either

- PRRT with ^{177}Lu -edotreotide consisting of a maximum of four cycles (7.5 ± 0.7 GBq ^{177}Lu -edotreotide, each), administered as IV infusion at 3-monthly intervals for 9 months, or until diagnosis of progression (200 patients), or
- 10 mg everolimus (Afinitor®) daily, administered orally as a tablet (100 patients).

Duration: Baseline: day -90 to -1

Randomisation: day -28 to -1

Treatment and study procedures: month 0 to 30, or until progression or withdrawal – whichever occurs earlier

EOS: month 30 or at progression or drop-out - whichever occurs earlier

Collection of survival and local disease progression data as well as information on further tumour treatments will be continued after EOS during the long-term follow-up.

Please refer to Section 3.1 of the current protocol for more details.

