For the sample size calculations, i.e. estimating the sample size, the power and/or the effect size, the following considerations were taken into account:

With regard to PFS, a two-sided logrank test with an overall sample size of $N=242$ subjects (180 events; randomised 1 : 2, $N_1=80$ subjects [68 events] in the everolimus group and $N_2=162$ subjects [112 events] in the ^{177}Lu -edotreotide group) achieves 80% power at a 5% significance level to detect a hazard ratio (HR) of 0.6471 when the everolimus group median survival time is 11 months (i.e., a difference of an additional 6 months in the ^{177}Lu -edotreotide group). The study was planned to last for 48 months of which subject accrual occurs in the first 24 months. The accrual across time is uniform. Of note, the trial sample size was not revised (i.e. decreased) after the protocol amendment that extended the patient follow-up from 24 months to 30 months.

Based on this HR a total sample size of 300 will compensate for a dropout rate (censored data) of 15% for primary endpoint analysis.

With regard to overall response rates, group sample sizes of 200 in the ^{177}Lu -edotreotide group and 100 in the everolimus group achieve 89% power to detect an odds ratio between the group ORRs of 4.2 (that corresponds to rates of 5% and 18%). The proportion in the ^{177}Lu -edotreotide group is assumed to be 5% under the null hypothesis and 18% under the alternative hypothesis. The proportion in the everolimus group is assumed to be 5% according to results of the RADIANT-3 study (Yao et al., 2011). The test statistic used is the two-sided Fisher's Exact Test. The significance level of the test is 5%. A dropout rate of 15% is included in this calculation using PASS software.

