With regard to overall survival, a two-sided logrank test with an overall sample size of $N=300$ subjects (198 events; randomised 1 : 2, $N_1=100$ subjects [76 events] in the everolimus group and $N_2=200$ subjects [122 events] in the ^{177}Lu -edotreotide group) achieves 80% power at a 5% significance level to detect a hazard ratio (HR) of 0.660 when the everolimus group median overall survival time is 44 months as in the RADIANT-3 study (Yao et al., 2016) (i.e., a difference of an additional 23 months in the ^{177}Lu -edotreotide group). The observation time for overall survival will be 5 years after EOS for all patients. The study duration was planned to last 48 months during which patient recruitment would take place in the first 24 months. The post-study follow-up period will then continue for another 5 years (60 months).

The sample size of 300 patients was chosen as the primary endpoint and the 2 key secondary endpoints are to be tested in a confirmatory manner. This sample size allows to address historically assumed PFS treatment effect (which would require 31 events) and minimal clinically relevant PFS difference (which would need 180 events).

In case a difference of 11 months in median PFS is observed ($m_1=11$ months versus $m_2=22$ months) the sample size also allows confirmation of PFS improvement for ^{177}Lu -edotreotide relative to reference treatment. This would need a total number of:

ITM-LET-01	Statistical Analysis Plan
-------------------	----------------------------------

- 205 events (E1=84 events in the everolimus group and E2=121 events in the ¹⁷⁷Lu-edotreotide group) with a power of about 99% and a two-sided level of significance of 1%
- or 156 events with a power of about 99% and a two-sided level of significance of 5%.
- or 67 events with a power of about 80% and two-sided level of significance of 5%.

In conclusion, the trial sample size of 300 randomized patients associated with the interim analysis plan at 90, 135 and 180 events (See Section 5.7) will allow to cover all the possible treatment effect assumptions at an overall two-sided alpha of 0.05 and with acceptable power (i.e. ≥80%; see Table 2).

Table 2: summary of PFS primary endpoint sample size assumptions

	Minimal clinically relevant difference	Historical treatment effect	Expected treatment effect		
Median PFS IMP	17	30	22		
Median PFS control	11	11	11		
Number of PFS events needed	180	31	67	156	205
Sample size (2:1)	242 (300 with dropout rate)	51	300		

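### SAP 5.7 gives ORR and OS no final look that spends their remaining alpha; OS is expected to stop short of 198 deaths and would then be tested below 5%

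*SAP*

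**What the plan says.** **Sizing (SAP 4).** The ORR calculation takes 200 and 100 patients, rates of 18% and 5%, two-sided Fisher, and claims 89% power: "The significance level of the test is 5%. A dropout rate of 15% is included in this calculation using PASS software". The OS calculation takes 198 deaths among 300 patients and "achieves 80% power at a 5% significance level to detect a hazard ratio (HR) of 0.660". Both are single-look calculations at the full 5%.

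**Testing (SAP 5.7).** After a significant PFS result, the ORR boundary is "calculated extemporaneously based on the number of evaluable patients at the time of the interim analysis compared to the 300 patients to be randomised". After a significant ORR result, the OS boundary is "calculated at the time of interim according to the number of OS events actually observed over an estimated total of 198 death events". Table 4 gives ORR levels of 0.0282 at 250 evaluable patients, 0.0407 at 280 and 0.05 at 300. Tables 4 and 5 are both labelled as examples for the first interim time point.

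**Closing rule.** For PFS, Table 3 gives a final level of 0.044 at 180 events, with the footnote "Or all randomized patients reach EOS". No final timing, final level or fallback is given for ORR or OS.

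**Follow-up (SAP 3.1 and 3.4.2; Protocol 7.4.1).** A patient's EOS is month 30, or progression or drop-out if earlier. Survival is followed for five years after EOS.

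**The concern.** The ORR and OS information fractions have fixed denominators, 300 and 198. If an endpoint's last analysis falls short of its denominator, the only formula in the SAP still holds alpha back, although no further data will come. That alpha protects nothing. Using it at the last look would leave the overall error at 5%.

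A confirmatory OS result could then miss significance only because alpha was kept for deaths that will not be observed. The hierarchy is strict, so an ORR miss for the same reason would make OS exploratory. If the last-look level is settled later, it would be chosen after the PFS result, and for OS the ORR result, is known.

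**Working it through.** **1. Spending function.** With t the information fraction, two-sided alpha(t) = 4 × [1 − Φ(z(0.9875)/√t)]. This reproduces Table 4:

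- t = 150/300: 0.0031
- t = 200/300: 0.0121
- t = 250/300: 0.0282
- t = 280/300: 0.0407
- t = 1: 0.05

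**2. The plan's OS power.** The Schoenfeld form is power = Φ(√(d × 2/9) × |ln 0.66| − z), where 2/9 = (1/3)(2/3) for 2:1 allocation. With d = 198 and z = 1.960: Φ(2.756 − 1.960) = 78.7%. Using the SAP's 76/122 event split as the weight gives 81.2%. The stated 80% is reproduced.

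**3. Where 198 deaths comes from.** The control median is 44 months, and the experimental median is 44/0.66 = 66.7 months. With everyone followed for 90 months (30 + 60):

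- everolimus: 100 × (1 − 0.5^(90/44)) = 75.8
- ¹⁷⁷Lu-edotreotide: 200 × (1 − 0.5^(90/66.7)) = 121.5
- total: about 197

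So 198 needs 90 months in every patient. Under the EOS definition, follow-up lies between 60 and 90 months. At 60 months throughout, the total is 61.1 + 92.8 = 154.

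**4. Deaths expected at EOS + 60 months.** I simulated exponential OS (44 and 66.7 months) and exponential PFS (11 months for everolimus; 17, 22 or 30 months for ¹⁷⁷Lu-edotreotide, the SAP Table 2 scenarios). The PFS/OS correlation is my assumption. There was no loss to follow-up.

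- correlation 0: 178 to 182 deaths
- correlation 0.8: 182 to 188 deaths

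**5. OS level and power from the stated formula.**

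| Deaths | t = d/198 | Level | Power at that level | Power at 5% |
|---|---|---|---|---|
| 170 | 0.859 | 0.0311 | 65.5% | 72.4% |
| 178 | 0.899 | 0.0362 | 69.8% | 74.3% |
| 180 | 0.909 | 0.0375 | 70.8% | 74.8% |
| 188 | 0.949 | 0.0429 | 74.6% | 76.6% |
| 198 | 1 | 0.05 | 78.7% | 78.7% |

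For 180 deaths: √(180 × 2/9) × 0.4155 = 2.628. Then Φ(2.628 − 2.081) = 70.8%, and Φ(2.628 − 1.960) = 74.8%. Of the 7.9 points lost from 78.7%, 3.9 come from fewer deaths and 4.0 from the level. The 170 row illustrates some loss to follow-up, for which the SAP states no OS rate.

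**6. What a closing rule recovers for OS.** Suppose an earlier OS look took place at 90 deaths (Table 5 level 0.0018). A full-spend final level is then at least 0.05 − 0.0018 = 0.0482. At 180 deaths, power is Φ(2.628 − 1.975) = 74.3% or a little more.

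**7. ORR, exact enumeration at 18% vs 5%.**

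| Patients | Level | Fisher (minimum-likelihood) | Mantel-Haenszel, unstratified |
|---|---|---|---|
| 200/100 | 0.05 | 91.5% | 92.3% |
| 170/85 | 0.05 | 86.7% | 87.4% |
| 170/85 | 0.0301 | 79.4% | 81.2% |

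170/85 is 300 × 0.85 = 255, so t = 0.85. Doubled-tail Fisher gives 89.9%, 83.7% and 77.5% for the three rows. With Fisher, the stated 89% is therefore matched only if dropout is not deducted from the 300. On a like-for-like test, the reduced level costs 6 to 7 points, and losing 45 patients costs about 5 to 6. If 15% stay in the FAS as non-responders (rates 15.3% and 4.25%), t = 1, the level is 0.05, and Fisher power is 83-85%.

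**The case against.** **The SAP does not exclude a full-spend final look.** Its ORR and OS text concerns interim analyses, Tables 4 and 5 are first-interim examples, ORR is to follow an approach similar to PFS, and overall alpha is 5%. All of this stands: a later look is implied. A reader might infer that the plan forbids spending the remainder, but the documents do not say so. The defect is an omission. Protocol 9.3.2 is redacted, so a rule there cannot be ruled out; SAP 5.7 is readable and contains none.

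**ORR power is not shown to be 81% instead of 89%.** A reader might infer that planned dropout has this effect. It would need 15% dropout to mean 15% not evaluable, and SAP 5.7 does not define evaluable. Confirmatory ORR uses the FAS, which is all randomised patients (SAP 5.2.1). A patient who leaves after one adequate scan can contribute a best response. Protocol 4.4.3 provides further enrolment for treated patients without analysable efficacy data. The fall from 89% to 81% also mixes patient loss, a change of test and the level.

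**The OS death count is modelled.** The documents give no joint PFS/OS distribution. SAP 4 also describes a 48-month study with 24 months of accrual, then 60 further months. Read as calendar time, follow-up is 84 to 108 months and about 204 deaths are expected, so nothing would be withheld. But SAP 3.4.2 and Protocol 7.4.1 count five years from EOS, and Protocol 7.4.1 does so for each patient. In addition, if at least 33% of control patients start new anticancer treatment or PRRT, SAP 6 makes the main OS analysis time-dependent, and the log-rank powers above are then only a guide.

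**The error is conservative.** There is no type I inflation, and PFS is untouched. That limits the severity but does not justify giving power away.

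**Conclusion.** The point holds, mainly for OS. With follow-up to EOS + 60 months, the plan's medians give about 178 to 188 deaths before loss to follow-up, so falling short of 198 is the expected case. Applied at the last look, the stated formula then gives levels of about 0.036 to 0.043 and power of about 70% to 75%. At 5% the same deaths give about 74% to 77%. The rule therefore costs roughly 2 to 4.5 points, and more if patients are lost. The rest of the gap to the stated 80% comes from fewer deaths, which no alpha rule restores. These figures assume exponential PFS and OS, a correlation of 0 to 0.8, and a standard log-rank test.

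For ORR the result is conditional. The level is 0.0301, with power of about 79-81% against about 87% at 5%, only if evaluable excludes dropouts and 255 patients remain. If all FAS patients count, the level is 0.05 and no alpha is withheld. Primary PFS inference and overall error control are not in question.

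**What to change.** In SAP 5.7:

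- State that the last ORR analysis takes place when all randomised patients have reached EOS. State that the last OS analysis takes place at 198 deaths or the end of the five-year follow-up, whichever comes first.
- Run both at information fraction 1, with the critical value recomputed to use all alpha not spent at that endpoint's earlier looks.
- Use the FAS as both the ORR analysis set and its information base, with non-evaluable patients counted as non-responders.

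In SAP 4:

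- Restate OS power for the deaths expected under EOS + 60 months: about 74-77% at 5% for 178 to 188 deaths, before loss to follow-up.
- Say whether the ORR figure of 89% is before or after the 15% dropout, and do not attribute a fall from it to the alpha rule alone.

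The cost is a few sentences and a boundary recalculation at the last look. No patients or data are added, and the overall two-sided error stays at 5%. The text should be settled before the endpoint results are known.
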